3.3 EXPLORATORY OBJECTIVES AND ENDPOINTS

Exploratory Objectives	Exploratory Endpoints
To further evaluate the effect of imsidolimab on AV signs and symptoms and quality of life in subjects with AV	
 Two-point decrease from Baseline in Facial IGA at each visit Change from Baseline in Truncal PGA for chest at each visit Change from Baseline in Truncal PGA for neck at each visit

Efficacy and Safety of Imsidolimab in Subjects with Acne Vulgaris
Protocol ANB019-209

Version 1.0
11 February 2021

Exploratory Objectives	Exploratory Endpoints
	
 Change from Baseline in Truncal PGA for back at each visit Proportion of subjects achieving a Truncal PGA for chest of clear (0) or almost clear (1) with at least a 2-grade decrease from Baseline at each visit Proportion of subjects achieving a Truncal PGA for neck of clear (0) or almost clear (1) with at least a 2-grade decrease from Baseline at each visit Proportion of subjects achieving a Truncal PGA for back of clear (0) or almost clear (1) with at least a 2-grade decrease from Baseline at each visit Proportion of subjects in each response category for the SSQ at each visit Proportion of subjects in each response category for the SSRS at Week 12 and Week 20 Change from Baseline in lesion counts based on blinded photographic assessment at each visit
To explore the effect of imsidolimab on cutaneous biomarkers	Assessment of biomarkers in tape strips
To test for immunogenicity to imsidolimab	Presence of anti-drug antibodies to imsidolimab
To describe the PK profile of imsidolimab in subjects with AV	Serum concentration following imsidolimab administration and other parameters as appropriate will be determined to describe the PK profile of imsidolimab

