9.4.7 ANALYSIS OF THE EXPLORATORY EFFICACY ENDPOINTS

Following are the exploratory efficacy endpoints:

- Two-point decrease from Baseline in Facial IGA at each visit
- Change from Baseline in Truncal PGA for chest at each visit
- Change from Baseline in Truncal PGA for neck at each visit
- Change from Baseline in Truncal PGA for back at each visit
- Proportion of subjects achieving a Truncal PGA for chest of clear (0) or almost clear (1) with at least a 2-grade decrease from Baseline at each visit
- Proportion of subjects achieving a Truncal PGA for neck of clear (0) or almost clear (1) with at least a 2-grade decrease from Baseline at each visit
- Proportion of subjects achieving a Truncal PGA for back of clear (0) or almost clear (1) with at least a 2-grade decrease from Baseline at each visit
- Proportion of subjects in each response category for the SSQ at each visit
- Proportion of subjects in each response category for the SSRS at Week 12 and Week 20
- Change from Baseline in lesion counts based on blinded photographic assessment at each visit

Efficacy and Safety of Imsidolimab in Subjects with Acne Vulgaris
Protocol ANB019-209

Version 1.0
11 February 2021

Methods for analyzing the above categorical and continuous efficacy endpoints will mirror the methods described in [Section 9.4.6.1](#) and [9.4.6.2](#), respectively.

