$$\frac{\text{Number of subjects with (overall Truncal PGA at Week } x - \text{overall Truncal PGA at baseline)} \leq -2}{\text{Number of subjects in treatment group with baseline overall Truncal PGA} \geq 2 \text{ and overall Truncal PGA at Week } x}$$

- **Proportion of subjects achieving a Truncal PGA for chest of clear (0) or almost clear (1) with at least a 2-grade decrease from Baseline at each visit**

For each treatment group, the number of subjects achieving a Truncal PGA for chest of clear (0) or almost clear (1) with at least a 2-grade decrease from baseline will be calculated at each visit (Weeks 2, 4, 8, 12, and 20). The proportion of such subjects will be calculated for each treatment group at each visit as:

$$\frac{\text{Number of subjects achieving a Truncal PGA for chest of clear (0) or almost clear (1) with baseline Truncal PGA for chest} \geq 2 \text{ at Week } x}{\text{Number of subjects in treatment group with baseline Truncal PGA for chest} \geq 2 \text{ and Truncal PGA for chest at Week } x}$$

- Proportion of subjects achieving a Truncal PGA for neck of clear (0) or almost clear (1) with at least a 2-grade decrease from Baseline at each visit**

For each treatment group, the number of subjects achieving a Truncal PGA for neck of clear (0) or almost clear (1) with at least a 2-grade decrease from baseline will be calculated at each visit (Weeks 2, 4, 8, 12, and 20). The proportion of such subjects will be calculated for each treatment group at each visit as:

$$\frac{\text{Number of subjects achieving a Truncal PGA for neck of clear (0) or almost clear (1) with baseline Truncal PGA for neck} \geq 2 \text{ at Week } x}{\text{Number of subjects in treatment group with baseline Truncal PGA for neck} \geq 2 \text{ and Truncal PGA for neck at Week } x}$$

- Proportion of subjects achieving a Truncal PGA for back of clear (0) or almost clear (1) with at least a 2-grade decrease from Baseline at each visit**

For each treatment group, the number of subjects achieving a Truncal PGA for back of clear (0) or almost clear (1) with at least a 2-grade decrease from baseline will be calculated at each visit (Weeks 2, 4, 8, 12, and 20). The proportion of such subjects will be calculated for each treatment group at each visit as:

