$$\frac{\text{Number of subjects achieving a Truncal PGA for back of clear (0) or almost clear (1) with baseline Truncal PGA for back} \geq 2 \text{ at Week } x}{\text{Number of subjects in treatment group with baseline Truncal PGA for back} \geq 2 \text{ and Truncal PGA for back at Week } x}$$

- Proportion of subjects achieving an overall Truncal PGA of clear (0) or almost clear (1) with at least a 2-grade decrease from Baseline at each visit for subjects with Baseline overall Truncal PGA score of at least 2**

For each treatment group, the number of subjects achieving an overall Truncal PGA of clear (0) or almost clear (1) with at least a 2-grade decrease from baseline will be calculated at each visit (Weeks 2, 4, 8, 12, and 20). The proportion of such subjects will be calculated for each treatment group at each visit as:

$$\frac{\text{Number of subjects achieving an overall Truncal PGA of clear (0) or almost clear (1) with baseline overall Truncal PGA} \geq 2 \text{ at Week } x}{\text{Number of subjects in treatment group with baseline Truncal PGA for back} \geq 2 \text{ and Truncal PGA for back at Week } x}$$

- Proportion of subjects achieving improvement (“Much better” or “Very much better”) according to the PGI-C at each post-Baseline visit**

For each treatment group, the number of subjects achieving improvement (“Much better” or “Very much better”) according to the PGI-C will be calculated at each post-baseline visit specified in the Schedule of Activities in **Table 2**. The proportion of such subjects will be calculated for each treatment group at each post-baseline visit (Weeks 2, 4, 8, 12, and 20) as:

$$\frac{\text{Number of subjects with PGI-C of “Much better” or “Very much better” at Week } x}{\text{Number of subjects in treatment group with PGI-C at Week } x}$$

- **Proportion of subjects achieving improvement (“A little better”, “Much better” or “Very much better”) according to the PGI-C at each post-Baseline visit**

For each treatment group, the number of subjects achieving improvement (“A little better”, “Much better” or “Very much better”) according to the PGI-C will be calculated at each post-baseline visit specified in the Schedule of Activities in **Table 2**. The proportion of such subjects will be calculated for each treatment group at each post-baseline visit (Weeks 2, 4, 8, 12, and 20) as:

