## **8.      CHANGES FROM METHODS PLANNED IN THE PROTOCOL**

The following exploratory analyses have been added:

- Change and percent change from Baseline in facial papule lesion counts at each visit
- Change and percent change from Baseline in facial pustule lesion counts at each visit
- Change and percent change from Baseline in facial nodule lesion counts at each visit
- Change from Baseline in overall Truncal PGA at each visit
- Proportion of subjects with at least 1-point decrease from Baseline in facial IGA at each visit

- Proportion of subjects with at least 1-point decrease from Baseline in overall Truncal PGA at each visit for subjects with Baseline overall Truncal PGA score of at least 1
- Proportion of subjects with at least 2-point decrease from Baseline in overall Truncal PGA at each visit for subjects with Baseline overall Truncal PGA score of at least 2
- Proportion of subjects achieving an overall Truncal PGA of clear (0) or almost clear (1) with at least a 2-grade decrease from Baseline at each visit for subjects with Baseline overall Truncal PGA score of at least 2
- Proportion of subjects achieving improvement (“Much better” or “Very much better”) according to the PGI-C at each visit
- Proportion of subjects achieving improvement (“A little better”, “Much better” or “Very much better”) according to the PGI-C at each visit
- Proportion of subjects achieving “Mild” or “Clear skin” according to the PGI-S at each visit
- Change from Baseline in PGI-S at each visit
- Proportion of subjects achieving “slightly satisfied”, “somewhat satisfied”, or “extremely satisfied” according to the SSQ at each visit
- Proportion of subjects achieving “slightly satisfied”, “somewhat satisfied”, or “extremely satisfied” according to the SSRS at Week 12 and Week 20
- Proportion of subjects achieving a DLQI of 0 or 1 at each visit for subjects with Baseline DLQI of at least 2
- Change from Baseline in PAS score based on blinded photographic assessment at each visit
- Change from Baseline in erythema score based on blinded photographic assessment at each visit

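### Four exploratory truncal PGA responder formulas in SAP 6.2.4 count a one-grade improvement as a response, and the overall one divides by a back-score population

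*SAP*

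**What the plan says.** **The intended rule.** In SAP Section 6.2.4 the chest endpoint is titled "Proportion of subjects achieving a Truncal PGA for chest of clear (0) or almost clear (1) with at least a 2-grade decrease from Baseline", and the sentence below the title repeats the condition. Neck, back and overall are worded the same way. The protocol gives the same rule for all three regions in its synopsis and in Sections 3.3 and 9.4.7, for example "Proportion of subjects achieving a Truncal PGA for back of clear (0) or almost clear (1) with at least a 2-grade decrease from Baseline" and "Proportion of subjects achieving a Truncal PGA for neck of clear (0) or almost clear (1) with at least a 2-grade decrease from Baseline". The overall endpoint was added by the SAP, and Section 8 lists it under the same rule: "Proportion of subjects achieving an overall Truncal PGA of clear (0) or almost clear (1) with at least a 2-grade decrease from Baseline". Section 8 declares no relaxation of the two-grade requirement.

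**The printed formulas.** The chest numerator is "Number of subjects achieving a Truncal PGA for chest of clear (0) or almost clear (1) with baseline Truncal PGA for chest" of at least 2. Neck and back have the same form. The overall numerator is "Number of subjects achieving an overall Truncal PGA of clear (0) or almost clear (1) with baseline overall Truncal PGA" of at least 2. None contains a term for the change from baseline.

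**The overall denominator.** It reads "Number of subjects in treatment group with baseline Truncal PGA for back" of at least 2, together with a back score at Week x. That is the denominator of the back endpoint printed just above it. The neighbouring overall endpoint for a drop of two or more points uses "Number of subjects in treatment group with baseline overall Truncal PGA" of at least 2, with an overall score at Week x.

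**The concern.** There are two separate faults. The numerators replace the size of the improvement by a minimum baseline, and the two conditions are not equivalent when the baseline can be 2. The overall endpoint also takes its numerator and denominator from different variables, so the responders need not be a subset of the subjects they are divided by.

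SAP Section 7.5.3 plans unadjusted risk differences, exact unconditional 90% intervals and CMH tests for these endpoints at each visit, overall and by facial IGA stratum. A programmer who follows the titles and one who follows the formulas will produce different results, and the SAP does not say which text governs.

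**Working it through.** No stated figure has to be reproduced here. The check compares each title with its formula over every possible score.

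**Inputs**
- Truncal PGA: 0 to 4, each region scored separately (Protocol 8.1.7, SAP 6.2.4).
- Overall truncal PGA: the mean of three regions mapped to a whole number by SAP Table 6 (0 if all are 0; 1 if below 1.5; 2 if below 2.5; 3 if below 3.5; otherwise 4).
- Eligibility: facial IGA must be 3 or 4, with no truncal minimum (Protocol 5.1). SAP 6.1.1 tabulates baseline truncal PGA over Grades 0 to 4, so a baseline of 2 is admissible.

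**Step 1: numerators**
- Formula: Week x score ≤ 1 and baseline ≥ 2. Accepted pairs: 2→0, 2→1, 3→0, 3→1, 4→0, 4→1 (six).
- Title: Week x score ≤ 1 and drop ≥ 2. Accepted pairs: 2→0, 3→0, 3→1, 4→0, 4→1 (five).
- The only difference is 2→1, a one-grade change.

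For the overall score, 2→1 needs only a one-grade change in one region. Baseline (2,2,1) has sum 5 and mean 1.67, so overall is 2; (2,1,1) has sum 4 and mean 1.33, so overall is 1.

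The facial IGA responder formula in SAP 6.2.3 has the same form. It is harmless for eligible subjects, because from a baseline of 3 or 4 any score of 0 or 1 is a drop of at least two grades.

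For a region, the excess response rate is (share of the denominator at baseline grade 2) × P(2→1). The documents give neither term. As pure assumption, shares of 25–75% and P(2→1) of 20–40% give 0.25 × 0.20 = 5 points up to 0.75 × 0.40 = 30 points. The documents do not support any value in that range over another.

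**Step 2: overall denominator**

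There are 5³ = 125 (chest, neck, back) combinations. By Table 6 the overall score is 0/1/2/3/4 in 1/34/55/31/4 of them.

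| Baseline set | Combinations |
|---|---|
| Overall ≥ 2 (title and numerator) | 55 + 31 + 4 = 90 |
| Back ≥ 2 (printed denominator) | 3 × 25 = 75 |
| Both | 65 |
| Overall ≥ 2, back < 2 | 90 − 65 = 25 (21 with overall 2, 4 with overall 3) |
| Back ≥ 2, overall < 2 | 75 − 65 = 10 (all with overall 1) |

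A subject in the group of 25, such as (3,3,1), can enter the numerator but never the denominator. A subject in the group of 10, such as (0,0,2), is in the denominator and can never respond.

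**Step 3: effect on the printed fraction**

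Take four subjects with baseline (2,2,2), two going to (0,0,0) and two unchanged. Title and formula both give 2/4 = 50%. Now vary this set; the title value stays at 2/4 throughout.

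| Change | Printed formula |
|---|---|
| One responder has baseline (3,3,1) instead | 2/3 = 67% |
| One non-responder has baseline (3,3,1) instead | 2/3 = 67% |
| One responder and both non-responders have baseline (3,3,1) | 2/1 = 200% |
| Add one subject (0,0,2)→(0,0,0) | 2/5 = 40% |
| One non-responder goes to (1,1,1), overall 2→1 | 3/4 = 75% |

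The first four rows show the denominator fault and the last the numerator fault.

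**The case against.** Four points can be made in the plan's defence.

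**Values above 100% would not reach the planned inference.** The template code in SAP Appendix 2 cross-tabulates one outcome per included subject, so responders are always a subset. If back ≥ 2 were programmed as the analysis subset, a (3,3,1) responder would leave both counts: the first row of the last table would be 1/3 = 33% and the third 1/1 = 100%. This stands. The 200% belongs to the printed fraction. The population analysed would still be the wrong one, and the numerator fault is untouched.

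**The planned shift tables allow recovery.** Section 7.5.3 plans them for each region and for the overall score, by arm and visit, in the manner of Section 7.5.2.7. Their cells hold the counts for the correct numerator and denominator of all four endpoints, so the title-based proportions and unadjusted risk differences can be rebuilt. The stratified results and CMH tests cannot. The correctly written overall two-point endpoint is also an upper bound on the true overall responder count. This stands as mitigation, but a reader would have to know that the reported proportions needed rebuilding.

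**The intent is obvious.** The rule appears twice above each formula, and the errors look like a reused template and a copying slip. That is probably right. It settles which text to correct; it does not make the formula safe to program from.

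**The endpoints are exploratory.** They are, without multiplicity control, and the primary, secondary and safety results are unaffected. This limits the importance of the point.

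**Conclusion.** The point holds. All four truncal numerators admit a 2→1 change that their titles, the protocol (for the regions) and SAP Section 8 (for the overall score) exclude. The overall endpoint's denominator is defined on the wrong variable.

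If the formulas are programmed, the numerator fault can only raise the three regional proportions or leave them unchanged. The overall proportion can move in either direction. The risk differences, intervals and CMH tests built on these proportions would carry the error. Its size in subjects, and its effect on treatment differences, cannot be determined, because no truncal baseline or transition distribution is given; the counts of 25 and 10 describe possible scores, not likely subjects. The conclusion rests only on a truncal baseline of 2 being possible and on the regional scores being free to differ, and both follow from the documents. It should be corrected, but it does not threaten the trial's main conclusions.

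**What to change.** Before programming, amend SAP Section 6.2.4 as follows.

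- **Numerators for chest, neck, back and overall:** score at Week x ≤ 1 and (score at Week x − baseline score) ≤ −2. The SAP already uses the difference form for its two-point endpoints.
- **Denominator for the overall endpoint:** baseline overall truncal PGA ≥ 2 with an overall truncal PGA at Week x, as in the neighbouring overall two-point endpoint.

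The accepted grade pairs then fall from six to five and match the titles. The overall responders become a subset of their denominator, so the proportion cannot exceed 1.

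The cost is SAP wording only: four numerators and one denominator, with no new data and no change to design or conduct. Regional response rates may be lower than under the printed formulas, and the overall rate may move either way, by an amount that cannot be known in advance.

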### 6.1 Demographic and Baseline Characteristics

#### 6.1.1 Demography and Physical Characteristics

Subject demographics will be summarized overall as well as by treatment arm. Additionally, baseline values of the efficacy measures for facial IGA, facial inflammatory/noninflammatory lesion counts, truncal physician's global assessment (PGA), patient-global impression of severity (PGI-S), dermatology life quality index (DLQI) total score, children's dermatology life quality index (CDLQI) total score, and subject satisfaction questionnaire (SSQ) will be summarized overall as well as by treatment arm in the baseline disease characteristics output.

Demographic and baseline characteristic variables summarized will include the following:

- Age
- Age group ([12, 18) years, [18, 30) years,  $\geq 30$  years)
- Age group ([12, 16) years,  $\geq 16$  years)
- Age group ([12, 25) years,  $\geq 25$  years)
- Sex
- Sex and Age group (Male and [12, 25) years, Male and  $\geq 25$  years, Female and [12, 25) years, Female and  $\geq 25$  years)
- Race
- Ethnicity (Hispanic or Non-Hispanic)
- Country
- Woman of childbearing potential (Yes or No)
- Smoking history
- Weight (kg)
- Height (cm)
- Body mass index (BMI; kg/m^2)
- Facial IGA at Baseline (Grade 3, Grade 4)
- Facial papule lesion counts at Baseline
- Facial pustule lesion counts at Baseline
- Facial nodule lesion counts at Baseline
- Facial papule and pustule lesion counts at Baseline
- Facial inflammatory lesion counts at Baseline
- Facial noninflammatory lesion counts at Baseline
- Total facial lesion counts at Baseline

- Truncal PGA (chest, back, neck, and overall) at Baseline (Grade 0 to Grade 4)
- PGI-S at Baseline (Grade 1 to Grade 4)
- DLQI total score at Baseline
- CDLQI total score at Baseline
- SSQ at Baseline (Grade 0 to Grade 6)

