$$\frac{\text{Number of subjects with PGI-C of “A little better”, “Much better” or “Very much better” at Week } x}{\text{Number of subjects in treatment group with PGI-C at Week } x}$$

- **Proportion of subjects achieving “Mild” or “Clear skin” according to the PGI-S at each visit**

For each treatment group, the number of subjects achieving “Mild” or “Clear skin” according to the PGI-S will be calculated at each visit specified in the Schedule of Activities in **Table 2**. The proportion of such subjects will be calculated for each treatment group at each visit (Weeks 0, 2, 4, 8, 12, and 20) as:

$$\frac{\text{Number of subjects with PGI-S of “Mild” or “Clear skin” at Week } x}{\text{Number of subjects in treatment group with PGI-S at Week } x}$$

- **Change from Baseline in PGI-S at each visit**

Change from baseline in PGI-S at each visit (Weeks 2, 4, 8, 12, and 20) will be calculated. The number and percentage of subjects who have PGI-S Grade 1, 2, 3, 4 at baseline and the shifts from baseline grades to each visit (Weeks 2, 4, 8, 12, and 20) will be calculated based on these values.

- **Proportion of subjects in each response category for the SSQ at each visit**

The SSQ asks subjects to rate their satisfaction with their acne condition on a 7-point scale from 0 (extremely dissatisfied) to 6 (extremely satisfied). It will be assessed at the visits specified in the Schedule of Activities in **Table 2**.

For each treatment group, the number of subjects in each response category for the SSQ will be calculated at each visit (Weeks 0, 2, 4, 8, 12 and 20). The proportion of such subjects will be calculated for each treatment group at each visit as:

$$\frac{\text{Number of subjects with SSQ of “extremely satisfied” at Week } x}{\text{Number of subjects in treatment group with SSQ at Week } x}$$

$$\frac{\text{Number of subjects with SSQ of “somewhat satisfied” at Week } x}{\text{Number of subjects in treatment group with SSQ at Week } x}$$

$$\frac{\text{Number of subjects with SSQ of “slightly satisfied” at Week } x}{\text{Number of subjects in treatment group with SSQ at Week } x}$$

$$\frac{\text{Number of subjects with SSQ of “neither satisfied nor dissatisfied” at Week } x}{\text{Number of subjects in treatment group with SSQ at Week } x}$$

$$\frac{\text{Number of subjects with SSQ of “slightly dissatisfied” at Week } x}{\text{Number of subjects in treatment group with SSQ at Week } x}$$

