$$\frac{\text{Number of subjects with SSQ of "somewhat dissatisfied" at Week } x}{\text{Number of subjects in treatment group with SSQ at Week } x}$$

$$\frac{\text{Number of subjects with SSQ of "extremely dissatisfied" at Week } x}{\text{Number of subjects in treatment group with SSQ at Week } x}$$

- **Proportion of subjects achieving “slightly satisfied”, “somewhat satisfied,” or “extremely satisfied” according to the SSQ at each visit**

For each treatment group, the number of subjects achieving “slightly satisfied”, “somewhat satisfied”, or “extremely satisfied” according to the SSQ will be calculated at each visit (Weeks 0, 2, 4, 8, 12 and 20). The proportion of such subjects will be calculated for each treatment group at each visit as:

$$\frac{\text{Number of subjects with SSQ of "slightly satisfied", "somewhat satisfied", or "extremely satisfied" at Week } x}{\text{Number of subjects in treatment group with SSQ at Week } x}$$

- **Proportion of subjects in each response category for the SSRS at Week 12 and Week 20**

The SSRS asks subjects to rate their satisfaction with their study treatment on a 7-point scale from 0 (extremely dissatisfied) to 6 (extremely satisfied). It will be assessed at Weeks 12 and 20.

For each treatment group, the number of subjects in each response category for the SSRS will be calculated at Weeks 12 and 20. The proportion of such subjects will be calculated for each treatment group at Weeks 12 and 20 as:

$$\frac{\text{Number of subjects with SSRS of "extremely satisfied" at Week } x}{\text{Number of subjects in treatment group with SSRS at Week } x}$$

$$\frac{\text{Number of subjects with SSRS of "somewhat satisfied" at Week } x}{\text{Number of subjects in treatment group with SSRS at Week } x}$$

$$\frac{\text{Number of subjects with SSRS of "slightly satisfied" at Week } x}{\text{Number of subjects in treatment group with SSRS at Week } x}$$

$$\frac{\text{Number of subjects with SSRS of "neither satisfied nor dissatisfied" at Week } x}{\text{Number of subjects in treatment group with SSRS at Week } x}$$

$$\frac{\text{Number of subjects with SSRS of "slightly dissatisfied" at Week } x}{\text{Number of subjects in treatment group with SSRS at Week } x}$$

$$\frac{\text{Number of subjects with SSRS of "somewhat dissatisfied" at Week } x}{\text{Number of subjects in treatment group with SSRS at Week } x}$$

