$$\frac{\text{Number of subjects with SSRS of "extremely dissatisfied" at Week } x}{\text{Number of subjects in treatment group with SSRS at Week } x}$$

- **Proportion of subjects achieving “slightly satisfied”, “somewhat satisfied”, or “extremely satisfied” according to the SSRS at Week 12 and Week 20**

For each treatment group, the number of subjects achieving “slightly satisfied”, “somewhat satisfied”, or “extremely satisfied” according to the SSRS will be calculated Week 12 and

Week 20. The proportion of such subjects will be calculated for each treatment group at each visit as:

$$\frac{\text{Number of subjects with SSRS of "slightly satisfied", "somewhat satisfied", or "extremely satisfied" at Week } x}{\text{Number of subjects in treatment group with SSRS at Week } x}$$

- **Proportion of subjects achieving a DLQI of 0 or 1 at each visit for subjects with Baseline DLQI of at least 2**

For each treatment group, the number of subjects achieving a DLQI of 0 or 1 with baseline DLQI of at least 2 will be calculated at each visit (Weeks 2, 4, 8, 12, and 20). The proportion of such subjects will be calculated for each treatment group at each visit as:

$$\frac{\text{Number of subjects achieving a DLQI of 0 or 1 with baseline DLQI } \geq 2 \text{ at Week } x}{\text{Number of subjects in treatment group with baseline DLQI } \geq 2 \text{ and DLQI at Week } x}$$

- **Proportion of subjects with less than 5 facial inflammatory lesion count (papules and pustules) at each visit**

For each treatment group, the number of subjects with less than 5 facial inflammatory lesion count (papules and pustules) will be calculated at each visit (Weeks 2, 4, 8, 12, and 20). The proportion of such subjects will be calculated for each treatment group at each visit as:

$$\frac{\text{Number of subjects with less than 5 facial inflammatory lesion count (papules and pustules) at Week } x}{\text{Number of subjects in treatment group with facial inflammatory lesion count (papules and pustules) at Week } x}$$

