### **7.5.3 Exploratory Efficacy Analyses**

The continuous data endpoints of change and percent change from baseline will be analyzed using the MMRM approach as described for the primary efficacy analysis in [Section 7.5.1](#). Summary statistics and the results of statistical testing at each visit will be provided for each continuous exploratory variable. In addition, the change from baseline in PGI-S and Truncal PGA (by body region as well as the overall and the worst score across three regions) will be summarized and analyzed by shift tables and ordinal logistic regressions as described in [Section 7.5.2.7](#). Baseline of the response variable will be added to the ordinal logistic regression model as a categorical variable. The overall Truncal PGA will be presented separately for all subjects, adolescents, and adults.

The frequency and percentage of subjects for subjects for categorical exploratory endpoints related to Truncal PGA (by body region as well as the overall and the worst score across three regions), facial IGA, PGI-C, PGI-S, SSQ, and SSRS will be summarized at each protocol-specified visit. For proportion of subjects in each response category for the SSQ and SSRS, the difference in distribution between each dose of imidolimab and placebo will be analyzed using the approach described for the proportion of subjects in each response category for the PGI-C in [Section 7.5.2.9](#). For other categorical exploratory endpoints, an unadjusted risk difference and 90% exact unconditional CIs will be estimated between each dose of imidolimab and placebo for all subjects and within each stratum for facial IGA at baseline (Grade 3 vs. 4); the common risk difference will also be tested using a generalized CMH test as described in [Section 7.5.2.8](#).

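### Exploratory PGI-S (Mild or Clear skin) and SSQ (satisfied) responder endpoints count subjects already at target at baseline; a baseline restriction, as the SAP uses for DLQI 0/1, is a cheap improvement

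*SAP*

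**What the plan says.** SAP 6.2.4 lists "Proportion of subjects achieving “Mild” or “Clear skin” according to the PGI-S at each visit" among the exploratory variables. The numerator is "Number of subjects with PGI-S of “Mild” or “Clear skin” at Week" x and the denominator is "Number of subjects in treatment group with PGI-S at Week" x, calculated "at each visit (Weeks 0, 2, 4, 8, 12, and 20) as" the ratio of the two. No change from baseline is required, and Week 0 is one of the visits.

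The SSQ endpoint in the same section has the same structure: "Proportion of subjects achieving “slightly satisfied”, “somewhat satisfied,” or “extremely satisfied” according to the SSQ at each visit", over everyone with an SSQ at the visit, Week 0 included.

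The DLQI responder endpoint in 6.2.4 is handled differently: "Proportion of subjects achieving a DLQI of 0 or 1 at each visit for subjects with Baseline DLQI of at least 2".

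Protocol 5.1 sets severity at entry by investigator-rated facial IGA (3 or 4) and by lesion counts. It has no PGI-S or SSQ criterion. SAP 6.1.1 plans to tabulate "PGI-S at Baseline (Grade 1 to Grade 4"), so it allows for Clear skin and Mild at baseline.

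Under SAP 7.5.3 these binary endpoints get an unadjusted risk difference with a 90% exact unconditional CI, and "the common risk difference will also be tested using a generalized CMH test" as set out in 7.5.2.8, where the only adjustment is for baseline facial IGA (Grade 3 vs. 4). The same section also analyses change from baseline in PGI-S with shift tables and an ordinal logistic regression that includes the baseline value.

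**The concern.** The endpoint is worded as something a subject achieves, but a subject who rates Mild on Day 1 meets it before the first dose. Such subjects add responses to every arm that carry little information on the drug, which pulls the risk difference towards zero. With arms of about 36 to 40, a chance difference between arms in the share at target on Day 1 also feeds into the observed difference. Neither the risk difference nor the IGA-stratified test takes account of baseline PGI-S or SSQ. At stake is the readability and sensitivity of two exploratory summaries. The primary endpoint and the sample size are not affected.

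**Working it through.** **Inputs from the documents.** 120 randomized 1:1:1 with 10% discontinuing before Week 12 gives 120 × 0.9 / 3 = 36 evaluable per arm (SAP 3.5). The level is two-sided 0.10 (SAP 3.3). The only power figure stated is for the primary endpoint: 80% for a 6.1-lesion difference with SD 10.4. It reproduces at n = 36: 80.1% by the normal approximation, 79.4% by the noncentral t. No figure is given for PGI-S or SSQ.

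**Assumptions, because the documents are silent.** q = share already Mild or Clear at baseline, 0 to 30%. r = share of those still Mild or Clear at Week x, 90% in every arm. p = response among subjects Moderate or Severe at baseline, 25% on placebo and 50% on active.

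**Dilution.** The rate in an arm is q·r + (1 − q)·p. With equal r, the difference between arms is (1 − q)(0.50 − 0.25).

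**Power.** Exact enumeration of the pooled two-proportion z-test at two-sided 0.10. For the restricted endpoint the calculation averages over the random number of eligible subjects per arm.

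| q | Active vs placebo, as written | Difference | Power as written | Power restricted |
|---|---|---|---|---|
| 0 | 50.0% vs 25.0% | 25.0 points | 73.8% | 73.8% |
| 5% | 52.0% vs 28.3% | 23.8 | 69.7% | 70.2% |
| 10% | 54.0% vs 31.5% | 22.5 | 65.5% | 68.1% |
| 20% | 58.0% vs 38.0% | 20.0 | 57.0% | 63.6% |
| 30% | 62.0% vs 44.5% | 17.5 | 48.5% | 58.6% |

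The restricted difference stays at 25 points throughout. The loss from leaving the endpoint unrestricted is about 0.6, 2.5, 6.5 and 10 points of power at q = 5%, 10%, 20% and 30%. A second scenario (30% versus 55%, r = 100%, normal approximation) gives 60.7 vs 65.7%, 52.3 vs 61.2% and 44.7 vs 56.2% at q = 10%, 20% and 30%. The direction is the same; the size depends on assumptions and method.

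**Chance imbalance.** The SD of the between-arm difference in baseline share is √(2q(1 − q)/36): 7.1, 9.4 and 10.8 points at q = 10%, 20% and 30%. With no drug effect, an imbalance enters the observed difference multiplied by (r − p) = 0.90 − 0.25 = 0.65. One SD therefore moves the estimate by 4.6, 6.1 and 7.0 points. At q = 20%, a difference of five or more subjects in either direction occurs in about 18% of trials; a difference of exactly five moves the estimate by 5/36 × 0.65 = 9.0 points.

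**Bias and type I error.** Averaged over randomization, both arms have the same expected rate under the null. The number of responders in each arm is then binomial with the same probability, so the error rate is that of an ordinary two-proportion test. Enumeration gives 9.7% to 12.3% over the q range; the departures from 10% come from the discreteness of an uncorrected z-test at 36 per arm.

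**When restriction costs power.** Let the drug also prevent worsening, with retention of 90% on active and 75% on placebo, at q = 20%. As written, the rates are 0.2 × 0.90 + 0.8 × 0.50 = 58% and 0.2 × 0.75 + 0.8 × 0.25 = 35%. Power is 67.0% as written against 63.6% restricted.

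**The case against.** The strongest reply is that the endpoint is a legitimate state prevalence. It collapses the secondary PGI-S category table (SAP 6.2.3), with the same denominator and the same Week 0 column, and baseline PGI-S is tabulated by arm, so an imbalance would be seen. The SAP also analyses change in PGI-S with shift tables and a baseline-adjusted ordinal model (7.5.3). All of this stands, and it limits the point. A reader might infer that baseline PGI-S is ignored throughout the plan; it is not. The companion analyses nevertheless leave the responder percentage, its CI and its p-value as they are, and the SSQ has no change-from-baseline analysis at all.

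A reader might also infer that the endpoint is biased or inflates false positives. The documents do not support that. Allocation is randomized, so imbalance is noise in a realised trial and does not favour either arm on average, and only about 0.65 of it reaches the estimate under the assumptions above.

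The appeal to consistency should be kept narrow. The facial IGA restriction to baseline 2 or more excludes nobody, because everyone enters at 3 or 4, and the facial and truncal responder endpoints are tied to a 2-grade decrease. DLQI 0/1 is the clean comparator.

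Finally, entry requires at least 20 inflammatory lesions and IGA 3 or 4, so q may be small. That is plausible but unknown; at q = 5% almost nothing is lost.

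**Conclusion.** The point holds as a cheap improvement to two exploratory endpoints. As defined, both count subjects already at target as having achieved it, and their planned tests do not account for the baseline rating. The expected risk difference shrinks by the factor (1 − q) if retention is equal across arms. Under the stated assumptions the power loss runs from under 1 point at q = 5% to about 10 points at q = 30%, and baseline imbalance adds noise of roughly 5 to 7 points per SD at q = 10% to 30%. All of this rests on an assumed q, because the documents report no baseline PGI-S distribution; if q = 0 there is no effect. The sizes are for PGI-S from a two-proportion test, not the stratified CMH test, and none was worked out for SSQ. Nothing here bears on the primary endpoint, the sample size or the type I error of the trial.

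**What to change.** In SAP 6.2.4, define the PGI-S responder endpoint at post-baseline visits as Mild or Clear skin at Week x among subjects with baseline PGI-S Moderate or Severe and a PGI-S at Week x. Treat the SSQ satisfied endpoint the same way, with baseline SSQ of 3 or less. Drop Week 0 from both, since the restricted proportion there is zero by construction. Keep the all-subject category proportions for PGI-S (6.2.3) and SSQ (6.2.4), so no information is lost from the report, and align the endpoint names in SAP Section 8.

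Alternatively, keep all subjects and add baseline status (at target or not) as a stratum in the CMH test. That adjusts the test only; the unadjusted risk difference and its CI would stay diluted.

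The cost is a few lines of SAP wording and no new data. The downsides are a smaller denominator, by the share already at target, and loss of any benefit from preventing worsening in baseline-Mild subjects, in which case restriction can cost a few points of power (67% to 64% in the example above).
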